### **7.1.6. Sensitivity Analyses**

All sensitivity analyses will include all subjects in the PITT population. Tabulated summaries of survival times, hazard ratios, and log rank test statistics as well as graphs of survival functions will be presented.

#### **7.1.6.1. Sensitivity Analyses**

Two sensitivity analyses (PFS-EP-2 and PFS-EP-3) to support the primary PFS analysis (PFS-EP-1) are shown in [Table 8](#). The two sensitivity analyses evaluate the impact of different assumptions or conditions that potentially influence the estimate of the primary estimand:

- The PFS-EP-2 definition evaluates the influence of potentially inconsistent tumor assessment intervals between arms. For subjects who experience radiographic progression, it assigns the date of the scheduled visit as the event date, rather than the date of recorded progression.
- The PFS-EP-3 definition evaluates the influence of the assessor of radiographic progression and is based upon RECIST 1.1 evaluations by the Investigator rather than the BIRC. This definition is used to assess the additional endpoint PFS per RECIST 1.1 as assessed by the Investigator.

**Table 8: Event and Censoring Rules for Primary and Sensitivity Analyses**

Estimand	Primary		Primary		Primary	
Analysis type	Primary		Sensitivity		Sensitivity	
Analysis purpose	Primary		Evaluate assessment time bias		Evaluate assessor bias	
Analysis ID	PFS-EP-1		PFS-EP-2		PFS-EP-3	
Analysis name	rPFS per BIRC		Uniform dates		rPFS per Investigator	
Estimand endpoint	Radiographic PD		Radiographic PD		Radiographic PD	
Population	PITT		PITT		PITT	
Situation	Outcome	Date of Outcome	Outcome	Date of Outcome	Outcome	Date of Outcome
Radiographic PD per RECIST 1.1 per BIRC	event	date of recorded PD	event	date of scheduled visit (or next scheduled visit if between visits)	NA	NA
Radiographic PD per RECIST 1.1 per Investigator	NA	NA	NA	NA	event	date of recorded PD
Death	event	date of death	event	date of death	event	date of death
Intercurrent events (excluding those with Treatment Policy strategy for all estimands)						
Clinical deterioration	NA	NA	NA	NA	NA	NA
Systemic NPACT (medications)	censored	date of last ATA* before first initiation of therapy	censored	date of last ATA* before first initiation of therapy	censored	date of last ATA* before first initiation of therapy
Local NPACT (medications)	NA	NA	NA	NA	NA	NA
Surgical resection of target tumor lesion(s)	censored	date of last ATA* before target lesion resection	censored	date of last ATA* before target lesion resection	censored	date of last ATA* before target lesion resection
Local radiation: to soft tissue for disease under study	censored	date of last ATA* before local radiation of soft tissue for disease under study	censored	date of last ATA* before local radiation of soft tissue for disease under study	censored	date of last ATA* before local radiation of soft tissue for disease under study
Missing data						
No baseline ATA	censored	date of rand.	censored	date of rand.	censored	date of rand.
≥ 2 consecutive missing scheduled ATA immediately prior to analysis event	censored	date of last ATA* before missing visits	censored	date of last ATA* before missing visits	censored	date of last ATA* before missing visits
Observation ongoing						
None of the above criteria for event or censoring	censored	date of last ATA*	censored	date of last ATA*	censored	date of last ATA*

ATA, adequate tumor assessment; BIRC, blinded independent review committee; ITT, intent-to-treat; NA, not applicable; PD, progressive disease; NPACT, non-protocol anticancer therapy (medications including radiopharmaceuticals but excluding local radiation); rPD, radiographic progressive disease per RECIST 1.1. For convention for date of recorded PD, see [Section 7.1.4](#).

\* or date of randomization if no post-randomization ATA  
Blue cells indicate changes from primary analysis.

### 7.1.6.2. Sensitivity Analyses to Evaluate Impact of Potential Informative Censoring

The four additional analyses (PFS-EP-11, PFS-EP-12, PFS-EP-13, PFS-EP-14) directed at the primary estimand will be conducted to evaluate the impact of potentially informative censoring. These analyses are based on the primary analysis PFS-EP-1 but with selected censored subjects re-classified as events, differentially by treatment arm, as shown in [Table 9](#). These are highly conservative definitions intended to evaluate potential bias. The directions of treatment effects are of key interest rather than the values of inferential statistics.

**Table 9: Definitions for Differential Sensitivity Analyses of PFS to Further Evaluate Potentially Informative Censoring (based on PFS-EP-1)**

Estimand	Primary							
Analysis type	Sensitivity							
Analysis purpose	Differential analyses to explore potentially informative censoring							
Analysis strategy	Selected censored subjects in primary analysis reclassified as events, differentially by assigned treatment arm, as shown below							
Analysis ID	PFS-EP-11		PFS-EP-12		PFS-EP-13		PFS-EP-14	
Censoring category for subjects censored in PFS-EP-1 in PITT Population	C+N+I	N+I	C+N+I	N+I	C+N+I	N+I	C+N+I	N+I
rPD per INV but not BIRC	At recorded date of first rPD per INV		At recorded date of first rPD per INV		At recorded date of first rPD per INV	At recorded date of first rPD per INV	At recorded date of first rPD per INV	
Discontinued radiographic assessment for reasons other than rPD and no sNPACT	At date of last ATA*		At date of last ATA*		At date of last ATA*		At date of last ATA*	
sNPACT prior to rPD per INV or BIRC			At date of first sNPACT	At date of first sNPACT			At date of first sNPACT	

ATA: adequate tumor assessment; BIRC: blinded independent review committee; Cntr: control arm; Exp: experimental arm; rPD: radiographic progressive disease per RECIST 1.1; INV: Investigator; sNPACT: systemic non-protocol anti-cancer therapy (medications including radiopharmaceuticals)

\* or date of randomization if no post-randomization ATA

### 7.1.7. Alternative Estimands

Four alternative estimands for PFS arising from changes in strategy for handling some intercurrent events are as defined below:

- Alternative estimand 1 changes the strategy for selected clinical intercurrent events to “composite,” resulting in an endpoint that includes as events earlier of either radiographic progression per BIRC, clinical deterioration, receipt of systemic non-protocol anti-cancer medications, receipt of radiation therapy to soft tissue for disease under consideration or surgical resection of target tumor lesions or death.

- Alternative estimand 2 changes the strategy to “composite” only for systemic non-protocol anti-cancer medications, yielding an endpoint that includes as events earlier of either radiographic progression (as well as death) or initiation of systemic NPACT.
- Alternative estimand 3 changes the strategy to “composite” for systemic non-protocol anti-cancer medications and missed tumor assessment yielding an endpoint that includes radiographic progression as well as death despite missed tumor assessments or initiation of systemic NPACT.
- Alternative estimand 4 changes the strategy to “composite” only for missed tumor assessment yielding an endpoint that includes radiographic progression as well as death despite missed tumor assessments.

More details are provided in [Table 10](#).

**Table 10: Alternative Estimands**

Estimand Attribute 	Event	Alternative 1 Definition	Alternative 2 Definition	Alternative 3 Definition	Alternative 4 Definition
Population		Subjects randomized into the study intended to include subjects with untreated advanced or metastatic RCC of intermediate or poor risk per IMDC (see Section 2.1 )			
Endpoint		Duration of radiographic and clinical progression-free survival	Duration of radiographic progression or initiation of systemic NPACT	Evaluate potentially informative censoring: Duration of radiographic progression despite missed 2 ATAs or initiation of systemic NPACT	Evaluate potentially informative censoring: Duration of radiographic progression despite missed 2 ATAs
		Strategy	Strategy	Strategy	Strategy
	Receipt of non-assigned study treatment	Treatment policy	Treatment policy	Treatment policy	Treatment policy
	Clinical deterioration	Composite	Treatment policy	Treatment policy	Treatment policy
	Receipt of local radiation to bone	Treatment policy	Treatment policy	Treatment policy	Treatment policy
	Surgical resection of non-target tumor lesions	Treatment policy	Treatment policy	Treatment policy	Treatment policy
Intercurrent events	Surgical resection of target tumor lesions	Composite	Hypothetical	Hypothetical	Hypothetical
	Receipt of systemic non-protocol anti-cancer medications	Composite	Composite	Composite	Hypothetical
	Receipt of local radiation to soft tissue for disease under study	Composite	Hypothetical	Hypothetical	Hypothetical
	Missed 2 or more adequate tumor assessments	Hypothetical	Hypothetical	Composite	Composite
Population summary		Difference in survival functions between treatment conditions as assessed by stratified log-rank test and characterized by the hazard ratio.			

Shaded cells differ from primary estimand.

See [Appendix E](#) for estimand terminology

#### 7.1.7.1. Supplemental Analyses

Event and censoring definitions are provided in [Table 11](#) for four supplemental analyses PFS-EA1, PFS-EA2, PFS-EA3, PFS-EA4 corresponding to alternate estimands PFS-EA1, PFS-EA2, PFS-EA3, PFS-EA4 for PFS respectively.

**Table 11: Event/ Censoring Rules for Supplementary Analyses of Alternative PFS Estimands**

Estimand	Alternative 1		Alternative 2		Alternative 3		Alternate 4	
Analysis type	Supplementary		Supplementary		Supplementary		Supplementary	
Analysis purpose	Alternate progression definition		Alternate progression definition		Evaluate potentially informative censoring		Evaluate potentially informative censoring	
Analysis ID	PFS-EA1		PFS-EA2		PFS-EA3		PFS-EA4	
Analysis name	Investigator claims		rPFS or sNPACT		rPFS or sNPACT despite missing ATA		rPFS despite missing ATA	
Estimand endpoint	Radiographic or clinical PD		Radiographic PD or initiation of systemic NPACT		Radiographic PD despite missed 2 ATAs or initiation of systemic NPACT		Radiographic PD despite missed 2 ATAs	
Population	PITT		PITT		PITT		PITT	
Situation	Outcome	Date of Outcome	Outcome	Date of Outcome	Outcome	Date of Outcome	Outcome	Date of Outcome
Radiographic PD per RECIST 1.1 per BIRC	NA	NA	event	date of recorded PD	event	date of recorded PD	event	date of recorded PD
Radiographic PD per RECIST 1.1 per Investigator	event	date of recorded PD	NA	NA	NA	NA	NA	NA
Death	event	date of death	event	date of death	event	date of death	event	date of death
Intercurrent events (excluding those with Treatment Policy strategy for all estimands)								
Clinical deterioration	event	date of determination of clinical deterioration	NA	NA	NA	NA	NA	NA
Systemic NPACT (medications)	event	date of first initiation of therapy	event	date of first initiation of therapy	event	date of first initiation of therapy	censored	Date of last ATA before systemic NPACT
Local NPACT (medications)	NA	NA	NA	NA	NA	NA	NA	NA
Surgical resection of target tumor lesion(s)	event	date of last ATA* before target lesion resection	censored	date of last ATA* before target lesion resection	censored	date of last ATA* before target lesion resection	censored	date of last ATA* before target lesion resection
Local radiation: to soft tissue for disease under study	event	date of last ATA* before local radiation	censored	date of last ATA* before local radiation	censored	date of last ATA* before local radiation	censored	date of last ATA* before local radiation
Missing data								
No baseline ATA	censored	date of rand.	censored	date of rand.	censored	date of rand.	censored	date of rand.
≥ 2 consecutive missing scheduled ATA immediately prior to analysis event	censored	date of last ATA* before missing visits	censored	date of last ATA* before missing visits	Event	date of last ATA* before missing visits	Event	date of last ATA* before missing visits
Observation ongoing								
None of the above criteria for event or censoring	censored	date of last ATA*	censored	date of last ATA*	censored	date of last ATA*	censored	date of last ATA*

ATA, adequate tumor assessment; BIRC, blinded independent review committee; ITT, intent-to-treat; NA, not applicable; PD, progressive disease; NPACT, non-protocol anti-cancer therapy (medications including radiopharmaceuticals but excluding local radiation)

For convention for date of recorded PD, see [Section 7.1.4](#).

\* or date of randomization if no post-randomization ATA

Blue cells indicate changes from primary analysis.

### 7.1.8. Exploratory Analyses

Exploratory analyses of the effect of baseline characteristics, stratification factors, and other variables on PFS may be conducted if necessary, using Cox regression models and subgroup analyses performed employing Kaplan-Meier methods. At the time of the primary analysis, PFS-EP-1 will also be repeated in the ITT population.

## 7.2. Secondary Efficacy Endpoint

The secondary efficacy endpoint for this study is duration of OS. Formal hypothesis testing is planned for this endpoint provided the null hypothesis of no difference between treatment arms for testing Primary PFS endpoint is rejected.

### 7.2.1. Estimand for Secondary Efficacy Endpoint of Overall Survival

The estimand for OS is the difference in survival functions between treatment conditions in the duration of survival in the targeted population:

- irrespective of whether the assigned study treatment was given
- irrespective of any subsequent therapy given

Estimands are derived as follows:

**Table 12: Estimand Definition and Rationale for Overall Survival**

Estimand attribute 	Primary definition		Rationale (as needed)
Population	Subjects randomized into the study intended to include subjects with untreated advanced or metastatic RCC of intermediate or poor risk per IMDC (see Section 2.1 )		The initial clause “Subjects randomized into the study intended to include...” is included to align the estimand with the application of the ITT principle expected by regulatory reviewers
Endpoint	Duration of overall survival		
Intercurrent events	Event	Strategy	Rationale (as needed)
	Receipt of non-assigned study treatment	Treatment policy	This strategy applied to align the estimand with the application of the ITT principle expected by regulatory reviewers.
	Receipt of any subsequent therapy	Treatment policy	
Population summary	Difference in survival functions between treatment conditions as assessed by stratified log-rank test and characterized by the hazard ratio.		

See [Appendix E](#) for estimand terminology

### **7.2.2. Definition**

Duration of OS (months) = (earliest date of death or censoring – date of randomization + 1)/30.4375.

General censoring rules for the analysis of OS are described below:

- For subjects who are alive at the time of data cutoff but are permanently lost to follow-up, duration of OS will be right censored at the date the subject was last known to be alive.
- Those who withdraw consent from survival follow-up and are alive will be right censored at the date the subject withdrew consent from survival follow-up.
- Subjects alive on or after the data cutoff or those who died after the data cutoff will be right censored at the date of data cutoff.

### **7.2.3. Primary Analysis**

The analysis of OS will include all subjects in the ITT population. Statistical methods used for analysis are as described for the primary endpoint of PFS (see details in [Section 7.1.5](#)).

The primary analysis of OS is planned to be conducted after a total of 433 deaths have been observed in the study. Three interim analyses of OS are planned at approximately the 27%, 50% and 75% IFs (see details in [Section 7.4.2](#)). If null hypothesis of no differences in OS is rejected at a planned interim OS analysis in favor of the experiment arm, no subsequent testing of OS is planned.

The analysis of OS will be performed amongst subjects in the ITT population provided the primary analysis of PFS is positive.

### **7.2.4. Exploratory Analysis**

Exploratory analyses of the effect of baseline characteristics, stratification factors, and other variables on OS may be conducted if necessary, using Cox regression models and subgroup analyses performed employing Kaplan-Meier methods.

## **7.3. Control of Type I Error and Timing of Analyses**

Inflation of Type 1 error associated with testing multiple endpoints (primary and secondary) will be controlled by applying a hierarchical testing procedure: The Primary PFS endpoint will be tested at 2-sided alpha of 5%. The secondary OS endpoint will be conducted at the same 5% alpha level only if the null hypothesis of no difference between arms in Primary PFS is rejected.

Three interim analyses of OS are planned at the 27%, 50%, and 75% IFs. The timing of the first interim OS analysis will coincide with the timing of the primary PFS analysis and will be conducted provided the null hypothesis for PFS is rejected in favor of the experimental arm. Type 1 error associated with interim analyses will be controlled using a Lan-DeMets O'Brien-Fleming alpha-spending function based upon a 5% total alpha allocation for OS (see details in [Section 7.4](#)).

All statistical evaluations of efficacy other than the primary or secondary endpoints will not be adjusted for the Type 1 error and the respective p-values will be considered as descriptive.

## 7.4. Interim Analyses

### 7.4.1. PFS Futility Analyses

A non-binding futility analysis of PFS is planned to be performed at the 40% IF (approximately 100 events). The futility boundary based on 100 events is 1.059 using a Lan-DeMets O'Brien-Fleming boundary and may have to be recomputed based on the actual number of events observed. The analysis will be based upon radiographic evaluations per the BIRC. Results will be reviewed by the IDMC as described as below:

- If the results of the futility analysis yield an observed HR for PFS per BIRC of  $< 1.059$  (and in the absence of significant safety concerns), the IDMC will recommend the trial continue.
- If the results of the futility analysis yield an observed HR for PFS per BIRC of  $\geq 1.059$ , the IDMC will refer the analysis results and a recommendation to a Sponsor Executive Committee (composed of individuals not involved in day-to-day trial conduct). The Executive Committee will review the analysis results and IDMC recommendation to take a decision about whether the trial will continue or be declared futile.
- If the trial is declared futile, study actions may include, but are not limited to discontinuing enrollment and/or discontinuing study treatment for study subjects.

The stratified HR and its 95% CI will be estimated using a Cox proportional-hazard model with treatment group as the independent variable.

### 7.4.2. OS Interim Analyses

Three interim analyses of OS are planned at approximately the 27% (estimated), 50% and 75% IFs based on a total alpha of 5% and are to be conducted only if the null hypothesis between treatment arms to test the Primary PFS endpoint is rejected. The timing of the first interim OS analysis is planned to coincide with the timing of the primary PFS analysis (estimated 27%

information fraction for OS) and will be conducted provided the null hypothesis for PFS is rejected in favor of the experimental arm. Details and boundaries for interim and the final analysis are shown in the [Table 13](#). The actual analyses may include more or fewer events than the target IFs, hence the actual critical values employed at the interim and final analyses of OS will depend upon the actual information fraction at the time of the analyses.

At an interim or final analysis, if the actual IF exceeds the planned IF due to faster than expected accrual or shorter than expected event times and/or event ascertainment lag, the analysis conducted per the information fractions shown in [Table 13](#) will be summarized descriptively as supportive analysis.

**Table 13: Details and Boundaries for the Interim and Final Analyses**

Critical Values for Testing OS		
OS alpha total	5.0%	
OS analysis information fraction	Critical p-value	Maximum HR to reject
IA1: 27%* (~117 death events)	0.0000324	0.464
IA2: 50% (~217 death events)	0.003	0.668
IA3: 75% (~325 death events)	0.018	0.77
FA: 100% (~433 death events)	0.044	0.824

\* The timing of the first interim OS analysis is planned to coincide with the timing of the primary PFS analysis (estimated 27% information fraction for OS) and will be conducted provided the null hypothesis for PFS is rejected in favor of the experimental arm.

IA, interim analysis; FA, final analysis.

Should the timing of the first interim analysis of OS (IA1) transpire at an information fraction much higher than expected (e.g. due to faster-than-expected deaths or slower-than expected PFS events), the interim analyses of OS will be conducted as follows.

**Table 14: Interim Analysis Strategy for OS**

OS IA1 IF	Proceed as	Rationale
<30%	perform IA1, IA2 and IA3 as planned	similar conditions to original plan
30 to < 40%	

• perform IA1 at time of primary PFS

• Conduct IA2 at 65% IF

• Do not conduct IA3

	Preserves two IA as planned with reasonable intervals between them
40 to < 50%	

• perform IA1 at time of primary PFS

• Conduct IA2 at 75% IF

• Do not conduct IA3

	Preserves two IA as planned with reasonable intervals between them
50 to 65%	

• perform IA1 at time of primary PFS

• Conduct IA2 to 80% IF

• Do not conduct IA3

	Preserves two IA as planned with reasonable intervals between them
$\geq 65\%$	

• Perform a IA1 at time of primary PFS

• Do not conduct IA2 and IA3

	IF is high enough that additional interims would not be practical

## 7.5. Additional Endpoints

Each exploratory endpoint will be analyzed using an appropriate two-sided statistical test without adjustment for multiplicity unless specified otherwise. Statistical results for exploratory endpoints will be considered supportive. Exploratory analyses will be performed on the ITT population unless specified otherwise.

### 7.5.1. Objective Response Rate (ORR) by BIRC

For each subject, best overall response (BOR) is defined as the best tumor assessment category as determined per RECIST 1.1 by BIRC that occurs through the first overall time point response of PD and prior to any of the censoring events defined for the primary analysis of PFS as described in [Section 7.1](#). Tumor assessment categories are ranked as: confirmed CR, PR, SD, progressive disease (PD) and not evaluable (NE). To be classified as confirmed CR or confirmed PR, confirmation must have occurred on a subsequent visit that is  $\geq 28$  days after the response was first observed. To be classified as SD, at least one overall time point response of SD must be documented  $\geq 56$  days after randomization. The ORR is defined as the proportion of subjects with a best response (BOR) of confirmed CR or confirmed PR.

Descriptive testing for ORR will be performed using an unstratified two-sided chi-squared test at 5% level of significance. If a sufficient number of responders are observed, analysis using the

Cochran-Mantel-Haenszel method to adjust for the stratification factors (see [Section 2.5](#)) will be generated.

Point estimates of ORR for each study treatment arm, the difference in ORR between the study treatment arms, and associated  $(1-\alpha)$  % confidence intervals will be provided. The odds ratio and associated  $(1-\alpha)$  % confidence intervals will also be presented. The 2-sided CIs for the point estimate of ORR will be calculated using the Clopper Pearson's method. The 2-sided CIs for the difference in ORR between the two study treatment arms and for the odds ratio will be calculated using asymptotic methods. All summaries for ORR will be provided for the ITT and PITT populations.

Time to objective response is an arithmetic summary amongst those with an objective response and is defined as time from randomization to the first CR or PR that is subsequently confirmed. Time to objective response will be summarized with descriptive statistics.

Waterfall plots displaying maximum percent tumor reduction since baseline in target lesions will be generated for tumor assessment data per BIRC.

These plots will include subjects with a tumor assessment at baseline and at least one post-baseline visit. For each subject, data on or after the progression/censoring date of the respective PFS analyses described in [Section 7.1](#) will be excluded from the waterfall plots.

A summary of the concordance between Investigator and IRC determined objective response status and date will also be provided.

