## TIME POINT RESPONSE CRITERIA

Target Lesion Time Point Response (TPR)	
Complete Response (CR)	Disappearance of all target lesions. All pathological lymph nodes (whether target or non-target) must have reduction in short axis to < 10 mm.
Partial Response (PR)	At least a 30% decrease in SoD of target lesions, taking as a reference the baseline SoD.
Stable Disease (SD)	Neither sufficient shrinkage to qualify for PR nor sufficient increase to qualify for PD.
Progressive Disease (PD)	At least a 20% increase in the SoD of target lesions, taking as a reference the smallest (nadir) SoD since (and including) baseline. In addition to the relative increase of 20%, the SoD must also demonstrate an absolute increase of at least 5 mm.
Not Applicable (NA)	No target lesion identified at baseline.
Unable to Evaluate (UE)	One or more target lesions are not imaged and the remainder of the SoD compared with the nadir SoD does not meet the criterion for PD.

SoD, baseline sum of diameters (longest for non-nodal lesions; short axis for nodal lesions).

If the target lesion for a subject meet the criteria for both PR and PD at a given time point, the target lesion response is PD.

If the nadir of SoD is 0 (ie, the subject had a prior target lesion CR), the reappearance of any prior target lesion to any degree constitutes PD.

Non-Target Lesion Time Point Response (TPR)	
Complete Response (CR)	Disappearance of all non-target lesions. All lymph nodes must be non-pathological in size (<10 mm short axis).
Non-CR / Non-PD	Persistence of one or more non-target lesion(s).
Progressive Disease (PD)	Unequivocal progression of non-target lesions. Unequivocal progression should normally not trump target lesion status. It must be representative of overall disease status change, not a single lesion increase.
Not Applicable (NA)	No non-target lesions identified at screening.
Unable to Evaluate (UE)	One or more non-target lesions are not imaged and the remaining non-target lesions do not meet the criterion for PD.

CONFIDENTIAL

Protocol XL184-313 Protocol Amendment 3.0  
Page 177 of 193

---

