### Evaluation of Overall Time Point Response

Target Lesion TPR	Non-target lesion TPR	New lesion TPR	Overall TPR
CR	CR or NA	No	CR*
CR	Non-CR/non-PD	No	PR*
CR	UE	No	PR*
PR	Non-PD or NA or UE	No	PR*
SD	Non-PD or NA or UE	No	SD
UE	Any except PD	No	UE
PD	Any	No or Yes	PD
Any	PD	No or Yes	PD
Any	Any	Yes	PD**
NA	CR	No	CR*
NA	Non-CR/Non-PD	No	Non-CR/non-PD
NA	UE	No	UE

CR, complete response; PR, partial response; SD, stable disease; PD, progressive disease, UE, unable to evaluate; NA, not applicable (no such lesions at screening); Any, CR, PR, SD, PD, NA, or UE.

The overall response at a given time point does not depend upon the overall response assigned at any prior or subsequent time point (ie, confirmation requirement is not considered when assigning time point responses).

\* Subjects with an overall response of CR or PR must have a follow-up tumor assessment performed no less than 4 weeks after the criteria for response are first met (this may be performed at the next scheduled tumor assessment). However, the presence, absence, or status at this follow up assessment is not considered when assigning a time point response at prior time points.

\*\* If a lesion disappears and reappears at a subsequent time point it should continue to be measured. However, the subject's response at the point in time when the lesion reappears will depend upon the status of his/her other lesions. For example, if the subject's tumor had reached a CR status and the lesion reappeared, then the subject would be considered PD at the time of reappearance. In contrast, if the tumor status was a PR or SD and one lesion which had disappeared then reappears, its maximal diameter should be added to the sum of the remaining lesions for a calculated response.

Furthermore, in order to identify potential delayed immune-mediated tumor response, subjects with an overall response of PD per RECIST 1.1 who continue with study treatment because of evidence of clinical benefit as assessed by the Investigator should have a follow-up tumor assessment no later than the next scheduled tumor assessment. However, the presence, absence, or status at this follow up assessment is not considered when assigning a time point response at prior time points.

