## **Best Overall Response**

Best overall response, incorporating confirmation requirements, will be derived during statistical analysis from the series of time point responses and need not be considered when assigning response at each time point.

CONFIDENTIAL

Protocol XL184-313 Protocol Amendment 3.0  
Page 180 of 193

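### SAP 7.5.1 classes an unconfirmed CR or PR with no separate SD time point as PD or NE rather than SD

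*SAP*

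**What the plan says.** SAP 7.5.1 defines best overall response (BOR) as the "best tumor assessment category as determined per RECIST 1.1 by BIRC that occurs through the first overall time point response of PD", restricted to the time before any of the PFS censoring events. Four further statements in that section fix the categories:

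- Ranking: "Tumor assessment categories are ranked as: confirmed CR, PR, SD, progressive disease (PD) and not evaluable (NE".
- Response: "To be classified as confirmed CR or confirmed PR, confirmation must have occurred on a subsequent visit that is" at least 28 days after the response was first seen.
- Stable disease: "To be classified as SD, at least one overall time point response of SD must be documented" at least 56 days after randomization.
- ORR: "The ORR is defined as the proportion of subjects with a best response (BOR) of confirmed CR or confirmed PR".

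SAP 7.5.2 applies the same method to Investigator assessments. Both versions are run in the ITT and PITT populations.

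The scan-level terms come from Protocol Appendix F. Target-lesion SD is "Neither sufficient shrinkage to qualify for PR nor sufficient increase to qualify for PD". The notes to the overall time point table add that the "confirmation requirement is not considered when assigning time point responses". On BOR, the appendix says only: "Best overall response, incorporating confirmation requirements, will be derived during statistical analysis from the series of time point responses". It gives no rule for a CR or PR that is never confirmed.

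Protocol 5.7.6.1 sets the first scan at W10D1 ± 7 days, then every 8 weeks through Week 50.

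**The concern.** The SD rule makes a documented SD scan a necessary condition. A scan that meets PR is by definition not an SD scan, and it is not recoded to SD when confirmation fails. A subject whose only evaluable scans before progression or censoring show CR or PR, without confirmation, therefore cannot be a responder and cannot be SD. The only categories left are PD, if progression follows, and NE if it does not.

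The order is then wrong. A subject with PR at Week 10 and PD at Week 18 shares a category with one who progressed at Week 10, and ranks below a subject who was merely stable at Week 10 and progressed at Week 18. Appendix F explains confirmation as a guard against overstating the response rate. Leaving the unconfirmed PR out of ORR serves that purpose; placing it below SD does not.

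At stake is the accuracy of the SD, PD and NE categories of a per-subject variable that the SAP defines for both BIRC and Investigator readings.

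**Working it through.** There is no stated figure to reproduce, because the point is a classification rule. The check applies the rule literally to possible scan sequences.

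**Timing.** W10D1 is 9 × 7 = 63 days after the start of the schedule. The earliest in-window scan is at 63 − 7 = 56 days. The 56-day condition is thus met by any in-window first scan, and only the requirement that the scan read SD can fail.

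**Examples at nominal Weeks 10, 18 and 26 (days 63, 119, 175):**

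| Sequence | Confirmed CR/PR? | SD scan at ≥ 56 days? | BOR as written | BOR if SD or better counts |
|---|---|---|---|---|
| PR, PD | no | no | PD | SD |
| CR, PD | no | no | PD | SD |
| PR only | no | no | NE | SD |
| PR, UE | no | no | NE | SD |
| PR, SD | no | yes | SD | SD |
| SD, PR, PD | no | yes | SD | SD |

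**All sequences of one to three scans.** Each scan is CR, PR, SD, PD or UE (unable to evaluate), and a sequence ends at the first PD. Write R for CR or PR (2 choices). Scheduled scans are 119 − 63 = 56 days apart, which exceeds 28. I count any second R as confirmation, allow an SD or UE scan in between, and treat CR followed by PR as a confirmed PR. A sequence with an unconfirmed response then contains exactly one R.

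- No SD, no PD (R with UE only): length 1 gives 2; length 2 gives 2 positions × 2 = 4; length 3 gives 3 × 2 = 6. Total 12, all NE.
- No SD, PD last: length 2 gives 2; length 3 gives 2 orders × 2 = 4. Total 6, all PD.
- At least one SD: length 2 gives 2 × 2 = 4; length 3 without PD gives 3 × 2 × (2² − 1) = 18; length 3 with PD last gives 2 × 2 = 4. Total 26, all SD.

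The sum is 12 + 6 + 26 = 44 patterns. The literal rule puts 12 + 6 = 18 of them in NE or PD.

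**After the change.** If an unconfirmed CR or PR at 56 days or later satisfies the SD condition, all 18 move to SD and the other 26 stay there. Responder status changes in none, because the SD condition matters only once a confirmed CR or PR has been ruled out.

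**The case against.** The strongest defense is that the SAP is silent rather than wrong. BOR is said to be determined per RECIST 1.1, no sentence sends unconfirmed responders to PD or NE, and a programmer might class them as SD by convention. This stands only in part. It is true that PD or NE follows from applying the rule, not from an explicit instruction. But the SD condition is explicit and necessary, and the protocol's own adaptation of RECIST 1.1 contains nothing that relaxes it, since it defers BOR to the analysis. The ranking adds to the doubt: 'confirmed' stands before CR and is not repeated before PR.

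A second defense is that the shrinkage is visible elsewhere. For PR at Week 10 and PD at Week 18, the waterfall plot in 7.5.1 would show the Week 10 reduction, because only data on or after the progression or censoring date are dropped. That holds for the PD pattern, although the plot then disagrees with the same subject's BOR. It does not clearly hold for a single PR followed by censoring: the censoring date in SAP Table 8 is the last adequate assessment, which is that PR scan.

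The third defense is about consequence, and it stands. ORR, time to response and duration of response use confirmed responses only. PFS and OS do not use BOR. Results for additional endpoints are supportive and unadjusted.

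A reader might infer more than the documents support:

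- **That every unconfirmed responder is demoted.** Not so; a subject with a qualifying SD scan is classed as SD.
- **That a disease control rate is understated, or one arm penalized.** The SAP defines no such rate and names no between-arm comparison of SD, PD or NE.
- **That data cutoff would leave many single-PR subjects in PITT.** SAP 4.8.1 gives a minimum follow-up of 15.6 months for the first 550 randomized, so cutoff is an implausible cause there. No minimum is stated for the remaining 840 − 550 = 290 ITT subjects.

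**Conclusion.** The rule is wrong as written for one defined group: subjects with an unconfirmed CR or PR and no separate SD time point at 56 days or later. They are classed as PD or NE although their disease was better than stable. In PITT the NE cases would come from systemic non-protocol therapy, another censoring event, drop-out or later unevaluable scans.

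The effect is confined to the descriptive SD/PD/NE split of BOR, per BIRC and per Investigator. No primary, secondary or formally tested result changes.

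The number of subjects cannot be given. The 18 of 44 is a count of possible patterns, not a share of patients, and the documents report no frequency of unconfirmed responses. For scale only, each 1% of subjects affected would be 550 × 0.01 = 5.5 in PITT and 840 × 0.01 = 8.4 in ITT. The conclusion assumes that the derivation follows the SAP literally and that scans fall in their windows. Severity: minor.

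**What to change.** In SAP 7.5.1, change the SD condition so that the documented time point response may be *SD or better (including unconfirmed CR or PR)*, keeping the limit of at least 56 days after randomization. In the ranking list, write *confirmed PR* in place of PR. Nothing need be added for non-CR/non-PD, because SAP 7.1.4 already groups it with SD.

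The cost is one phrase and one word in the SAP and one line in the BOR derivation. No new data are needed, ORR does not change, and I see no downside. SAP 7.5.2 takes its method from 7.5.1, so the Investigator version follows without a separate edit.
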